
Measures:

Baseline visit after consent and enrollment in the study. Data collection will include:

Physical Activity Vital Sign (PAVS): 3 questions as described above when patients check in for their clinical appointment.

Stages of Change will be assessed with a Readiness to Change Ruler.³¹ A straight line is drawn on paper representing the process of change (from 1= 'not ready to change' to 10='already changing').

Cardiorespiratory fitness (CRF) will be measured by the six-minute walk test, a valid and reliable measure for use in field testing of CRF.³² The 6MWT will be conducted in a quiet hallway using a 30-meter track with standard instructions.³³

BMI will be calculated by height and weight measured at the time of the Center visit on a balance beam scale.

Waist Circumference will be measured to the nearest inch using standard technique.³⁴ Blood pressure (BP) will be measured in right arm (unless contraindicated) after sitting for 5 minutes and repeated after a 5-minute interval. Both will be recorded and the average used in analyses.

CONFIDENTIAL

This material is the property of the NYU School of Medicine and Langone Medical Center. Do not disclose or use except as authorized in writing by the study sponsor
Interventional Template Version: 11 January 2019

Total cholesterol, HDL, and triglycerides will be measured by CLIA-waived Alere Cholestech LDX® Analyzer which is certified by the Center for Disease Control's Lipid Standardization Program and Cholesterol Reference Method Laboratory Method Network. This will be measured by a single fingerstick using standard aseptic technique.

The Framingham Heart Study Risk Score (10-year risk) will be calculated using the appropriate risk model based on participants' age, gender, diabetes status and prior coronary heart disease.³⁵ Two covariates that have an inverse association with PA, depressive symptoms and general health-related quality of life,^{36,37} will be assessed.

Depressive symptoms will be measured by the PROMIS Depression Short Form 6a, a reliable ($\alpha = .92$) 6-item survey with strong convergent validity ($\alpha = .72-.84$) which assesses negative views of self, social cognition, decreased positive affect and engagement³⁸ and is also available in Spanish.³⁹ It will be scored with REDCap auto-score.

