General health-related quality of life will be measured by the common data element 36-Item Short Form Health Survey (SF-36) v-1, a reliable measure ($\alpha = .90$) of physical and mental health with strong criterion validity, which is also available in Spanish.⁷⁷⁻⁸⁰ PROMIS surveys will be scored using the REDCap auto score for accuracy.

Clinical data will be collected from the EHR including potential confounding variables: age, sex, race/ethnicity, primary diagnosis, smoking status, and comorbidities (summarized as continuous data by the Charlson Comorbidity Index).⁴⁰

Sociodemographics, collected using common data elements survey⁴¹ and clinical data from the EHR will be collected at baseline. Fitbit steps will be collected daily for 3 months.

All other data will be collected baseline and at 3 months.

In the event all data collection must be remote or the subject prefers remote data collection, the PI will use baseline data from the electronic health record. The six-minute walk test can be administered remotely via an app on the subject's mobile phone with the distance walked emailed to the PI. BMI and blood pressure taken on the day of their recent clinical visit will be used for baseline data. A measuring tape will be mailed to the participant with instructions on measurement of waist circumference using standard technique. The PI or RA can schedule a videoconference to review the technique of measuring waist circumference. The most recent total cholesterol, HDL, and triglycerides results from the EHR will be used. All other baseline data collection will remain as planned.

If at 3-months remote data collection continues for a subject, the six-minute walk test will be done remotely with the mobile app. BMI and blood pressure will be used from the most recent office visit, as close to the 3-month follow-up date as possible. The patient will measure waist circumference as directed using standard technique and reviewed via video conference. The next available lab data for total cholesterol, HDL and triglycerides will be used. All other 3-month data collection will remain as planned.

If at 3-months in-person data collection is possible, the PI will resume in-person data collection as planned and meet the subject at the preventive cardiology center for data collection.

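### Participants with a remote baseline who return in person at 3 months have 6MWT, waist, lipid and possibly BP changes that mix two measurement methods, and the analysis does not separate these pairs

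*Combined protocol and SAP*

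**What the plan says.** Section 6.1.1 (Measures) makes in-person collection the default. The 6MWT is "conducted in a quiet hallway using a 30-meter track with standard instructions", waist is measured to the nearest inch, lipids come from a fingerstick on a point-of-care analyzer, and BP is the average of two seated readings taken five minutes apart.

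The same section opens a remote route: "In the event all data collection must be remote or the subject prefers remote data collection", baseline data come from other sources. "The six-minute walk test can be administered remotely via an app" on the participant's phone, with the distance emailed to the PI. For waist, "A measuring tape will be mailed to the participant with instructions on measurement of waist circumference". BMI and BP are those from the day of the recent clinic visit. For lipids, "The most recent total cholesterol, HDL, and triglycerides results from the EHR will be used".

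At 3 months there are two branches. If remote collection continues, the app walk and self-measured waist are repeated, "BMI and blood pressure will be used from the most recent office visit, as close to the 3-month follow-up date as possible", and "The next available lab data for total cholesterol, HDL and triglycerides will be used". Otherwise: "If at 3-months in-person data collection is possible, the PI will resume in-person data collection as planned and meet the subject".

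Section 9.1 tests changes in 6MWT, BMI, waist, BP, lipids and Framingham score with paired t-tests and reports the percentage of participants gaining 25 m on the 6MWT. Sections 9.1 to 9.2.2 contain no mode indicator, no same-mode restriction and no sensitivity analysis by mode. The exploratory regression has change in physical activity as its outcome, so it does not address these measures.

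**The concern.** The protocol keeps the method constant only for participants who stay remote. A participant with a remote baseline who can attend at 3 months changes method by design, not by deviation. Any systematic difference between methods then enters that participant's change score.

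These measures are primary endpoints (section 4.2.1), and section 9.2 describes the study's product as preliminary effect sizes. With one group and no comparator, an offset cannot cancel between arms. It passes into the mean change in proportion to the share who switch. The responder percentage is exposed too: a switched participant with no true change and a 25 m offset would sit exactly at the threshold.

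Fitbit step counts do not depend on the visit mode and are unaffected. BMI is not part of this point, because the in-person method also uses height and weight measured at the Center visit.

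**Working it through.** **Methods in a switched pair (section 6.1.1)**

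| Measure | Remote baseline | In-person 3 months |
|---|---|---|
| 6MWT | Phone app, distance emailed | 30-meter hallway track |
| Waist | Self-measured, mailed tape | Measured at the visit |
| Lipids | Most recent record result | Fingerstick analyzer |
| BP | Clinic-visit reading, technique not stated | Mean of two seated readings |
| Framingham score | Inherits the lipid and BP sources | Inherits the lipid and BP sources |

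The first three rows clearly differ. BP differs only if the clinic reading was taken by another technique.

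**Inputs from section 9.3.** 47 evaluable participants; effect size 0.41 tied to 28 m; effect size 0.33 tied to 25 m at 59 participants; type I error 5%; power 80%; sidedness not stated.

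**The plan's own figure.** A paired t-test with n = 47 and d = 0.41, two-sided, has power 78.6% by the noncentral t and 80.3% by the normal approximation, so the stated figure reproduces approximately. The implied SD of change is 28/0.41 = 68.3 m or 25/0.33 = 75.8 m. Both are used below. The standard error at n = 47 is 68.3/√47 = 9.96 m or 75.8/√47 = 11.05 m.

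**Assumed inputs.** The share f of analysed pairs that switch and a constant app-to-track offset b are not in the documents. All values of f and b are hypothetical.

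**Formulas, with no true change**
- Bias in mean change = f × b.
- Variance of change = SD² + f(1 − f)b².
- Rejection probability: noncentral t, 46 degrees of freedom, 5% two-sided (approximate, since a mixture is not exactly normal).
- Responder share = f·P(Z ≥ (25 − b)/SD) + (1 − f)·P(Z ≥ 25/SD).

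For example, f = 20% and b = 15 m gives bias 0.20 × 15 = 3 m, which is 3/25 = 12% of the 25 m threshold. The added variance is 0.2 × 0.8 × 225 = 36, so the SD barely changes (68.3 to 68.6 m).

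| f × b | Bias | % of 25 m | Two-sided rejection |
|---|---|---|---|
| 10% × 5 m | 0.5 m | 2% | 5.0% |
| 20% × 10 m | 2 m | 8% | 5.4% |
| 20% × 15 m | 3 m | 12% | 5.8–6.0% |
| 25% × 25 m | 6.25 m | 25% | 8.5–9.3% |
| 40% × 30 m (extreme) | 12 m | 48% | 18–21% |

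The responder share with no switching is 35.7–37.1%. It becomes 37.4–38.6% at 20% × 15 m (up 1.5–1.7 points) and 42.6–43.3% at 40% × 30 m (up 6–7 points).

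Two-sided rejection reaches 10% only at a bias of 6.6–7.4 m. That needs an offset of 6.6/0.2 = 33 m to 7.4/0.2 = 37 m if 20% switch, or 66–74 m if 10% switch.

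If the test were one-sided, 20% × 15 m would give 8.4–8.9% when the offset favours follow-up, and below 5% when it runs the other way.

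**Waist.** An assumed 1-inch offset (the recording unit) in 20% of pairs gives 0.2 × 1 = 0.2 inch.

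**The case against.** In-person collection is the default and the remote route is a contingency. The share who switch and the offset are unknown in size and sign, and moderate assumptions move the 6MWT by only 2 to 3 m. That stands, and it limits the severity.

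An uncontrolled pre-post pilot cannot attribute any change cleanly to the intervention, so mode is one more caveat among several. That is also fair. But this caveat, unlike most of the others, can be examined at little cost.

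The case report forms and the manual of procedures are not in the documents, and app distances, laboratory results and fingersticks come from distinguishable sources. A reader might infer that mode will go unrecorded. The documents show only that the visit lists and the schedule of events do not ask for it; it may be recoverable. What is missing for certain is a planned analysis that uses it.

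A reader might also infer that baseline BMI or BP could be re-entered as the 3-month value, since the most recent office visit is not expressly required to post-date baseline. The text does not support that reading. It asks for the visit nearest the 3-month date, section 6.1.2 says routine cardiology visits continue, and the laboratory wording points forward to the next result. A later value is plainly intended, so at most the wording needs clarifying.

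Finally, same-mode pairs are selected by whether in-person follow-up was possible. This stands: the subset is a sensitivity check, not an unbiased replacement.

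**Conclusion.** The point holds at low-to-moderate severity. Followed as written, the protocol pairs different methods for participants who switch, and the analysis does not separate those pairs. The text settles this for 6MWT, waist and lipids. For BP, and for any Framingham score built on these values, it is only possible.

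The size cannot be fixed from the documents. Under an assumed 20% × 15 m, the 6MWT bias is 3 m (d = 3/75.8 to 3/68.3, about 0.04) with about 6% two-sided rejection. Only the extreme 40% × 30 m produces 12 m (d = 12/75.8 to 12/68.3, or 0.16–0.18) and 18–21%. These figures assume a constant offset, approximately normal changes and the SDs implied by section 9.3.

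A reader might infer that the type I error is seriously inflated, or that the bias favours the intervention. Neither follows. Modest shares barely move the two-sided test, and an offset could run in either direction. The concern is the preliminary estimates and the responder percentage.

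**What to change.** 1. Record collection mode and measurement date for every baseline and 3-month value of 6MWT, waist, BP and lipids.
2. Keep the all-pairs analysis in section 9.1 as planned.
3. Pre-specify a sensitivity report of change in 6MWT (including the 25 m responder percentage), waist, BP, lipids and Framingham score in same-mode pairs. Give the number and baseline characteristics of switched pairs beside it.
4. At most, add a sentence that remote follow-up values taken from the health record must post-date baseline, and report their timing. Excluding values outside the ±2-week visit window is not needed; it would make routine-care values missing selectively.

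**Cost.** Two data fields, a few sentences of text and one extra table, with no added measurement for participants. In the same-mode subset the standard error rises by 1/√(1 − q) for an excluded share q: 1.05, 1.12 and 1.29 at 10%, 20% and 40%, or about 5%, 12% and 29%. The all-pairs analysis loses nothing.

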6.1.2 Standard of Care Study Procedures

Patient subjects will continue to see their cardiologists for routine clinical care according to their diagnosis.

CONFIDENTIAL

This material is the property of the NYU School of Medicine and Langone Medical Center. Do not disclose or use except as authorized in writing by the study sponsor
Interventional Template Version: 11 January 2019

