Participant Duration	Each participant will be in the study for 3 months. Baseline data collection is at Time 1; followed wearing the Fitbit for 3 months; and follow-up data collection at Time 2 (3 months).

CONFIDENTIAL

This material is the property of the NYU School of Medicine and Langone Medical Center. Do not disclose or use except as authorized in writing by the study sponsor

Interventional Template Version: 11 JAN 2019

Population	We will recruit 59 males and females age > 18 being seen in the NYU Langone Center for Prevention of Cardiovascular Disease (4F). Participants have cardiovascular disease or cardiovascular disease risk factors.
Study Site	NYU Langone Center for Prevention of Cardiovascular Disease (4F)
Number of participants	59 participants in one site
Description of Study Agent/Procedure	The intervention consists of physical activity assessment promotion and remote home step-count monitoring in a clinical cardiology center.
Reference Therapy	This is a one-group study. There is no comparison group.
Key Procedures	Key procedures include assessment of physical activity; counseling by the cardiologist if physical activity levels are <50% of recommended; remote home monitoring via Fitbit sync to MyChart.
Statistical Analysis	Paired t-tests will be used to assess changes in average PA from week 2 to three-month follow-up using PAVS and Fitbit Zip data. Paired t-tests will be used to assess changes in readiness to change number, the 6MWT, BMI, waist circumference, systolic and diastolic BP, lipids, and Framingham Heart Study Risk Score. To assess meaningful improvement in CRF, we will report the percent of participants who achieve a clinically important difference of 25 meters in the 6MWT. Bivariate analyses will compare all CVD risk factors, as well as other potential confounders (e.g. age, sex, race/ethnicity, depressive symptoms, comorbidities), between those who achieve PA recommendations and those who do not. Preliminary effect sizes of change in PA (step counts) will be generated following the Physical Activity Change Detection (PACD) approach. Aim 2 is to conduct a process evaluation of the intervention. Implementation data will be evaluated using the PRISM framework.

CONFIDENTIAL

This material is the property of the NYU School of Medicine and Langone Medical Center. Do not disclose or use except as authorized in writing by the study sponsor
Interventional Template Version: 11 January 2019

Flow diagram Single Group

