3.1 Primary Objective

Aim 1: Test the preliminary clinical efficacy of a PA promotion intervention on patients' cardiovascular risk profile (PA, cardiorespiratory fitness, BMI, waist circumference, blood pressure, lipids and Framingham Heart Study Risk Score).

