4.2 Study Endpoints

4.2.1 Primary Study Endpoints

For this feasibility study, we will implement the intervention (PA assessment using the PAVS; counseling by the cardiologists; and PA monitoring of patients wearing a Fitbit) for 12 months. Patient subjects who enroll in the PA monitoring will wear the Fitbit for 3 months. Primary endpoints include: patients' cardiovascular risk profile (PA, cardiorespiratory fitness, BMI, waist circumference, blood pressure, lipids and Framingham Heart Study Risk Score).

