5.9.3 Assessment of Subject Compliance with Study Intervention

If the patient subject has less than 5 days of valid Fitbit wear (less than 10 hours/day) for the week, the PI or RA will call the patient subject and discuss strategies to improve adherence. We will utilize the resources of the NYU Recruitment and Retention Unit as needed. We will follow up with the patient subjects with the method they prefer (phone, email, text) for Fitbit data collection and to schedule the follow-up data collection at 3 months.

6 Study Procedures and Schedule

Baseline visit: After their visit with their cardiologist, interested patient subjects will have the study described and consent and enrollment in the study if desired. Baseline data collection will take place. For the next 3 months the patient subject is asked to wear the Fitbit and sync to their app on their phone. At 3 months patient subjects will return to the clinic for follow-up assessment.

A sample of 10 patient subjects will be asked to provide feedback about the study at this follow-up visit. A semi structured interview guide will be used to obtain feedback about the intervention from their perspective. Upon study completion, qualitative interviews using a semi-structured interview guide with the three cardiologists and the one nurse practitioner in the Center who works with one of the cardiologists will explore the acceptability, clinical utility and usability of the implementation.

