9.1 Statistical and Analytical Plans (SAP)

Aim 1. Analysis will be performed using SAS 9.4. Surveys will be administered using the Research Electronic Data Capture (REDCap) system,⁴² a secure web-based tool licensed and supported by NYU. Standard descriptive statistics will be used to describe baseline sociodemographic and clinical characteristics. Mean scores and standard deviations as well as Cronbach's α will be calculated on questionnaires to confirm reliability of study instruments in our sample. Week 2 of the Fitbit Zip PA data will be used as baseline to assure the participant is accustomed to the device and to minimize the effect of reactivity, which can last approximately one week.⁴³ To calculate total minutes/week of PA from PAVS, the following standard calculation will be used:⁴⁴ light activity will be multiplied by 0 (light activity is not included in PA recommendations but is collected to acknowledge all attempts at PA and encourage increased intensity); moderate activity is multiplied by 1; vigorous activity is multiplied by 2 (one minute of vigorous activity being equal to two minutes of moderate activity). Paired t-tests will be used to assess changes in average PA from week 2 to three-month follow-up using PAVS and Fitbit Zip data. Using Fitabase software which allows for high resolution data, we will compare minutes of PA in three levels of intensity (light, moderate, and vigorous) as well as minutes spent in sedentary behavior. We will report the percentage of weeks each participant achieves the recommended levels of PA during the monitoring period and will assess weekly PA trends. We will compare improvements in PA by levels of protocol adoption by the HCP (e.g. 100% vs. 50% adoption). At 3 months we will compare mean minutes of moderate-to-vigorous PA between those who report achieving recommended levels of PA by the PAVS to those who do not. Paired t-tests will be used to assess changes in readiness to change number, the 6MWT, BMI, waist circumference, systolic and diastolic BP, lipids, and Framingham Heart Study Risk Score. To assess meaningful improvement in CRF, we will report the percent of participants who achieve a clinically important difference of 25 meters in the 6MWT.⁴⁵ Bivariate analyses will compare all CVD risk factors, as well as other potential confounders (e.g. age, sex, race/ethnicity, depressive symptoms, quality of life, comorbidities), between those who achieve PA recommendations and those who do not.

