13.1 Data Collection and Management Responsibilities

CONFIDENTIAL

This material is the property of the NYU School of Medicine and Langone Medical Center. Do not disclose or use except as authorized in writing by the study sponsor
Interventional Template Version: 11 January 2019

Data collection is the responsibility of the PI and the RA under the supervision of the PI. The investigator is responsible for ensuring the accuracy, completeness, legibility, and timeliness of the data reported.

All source documents should be completed in a neat, legible manner to ensure accurate interpretation of data. Black ink is required to ensure clarity of reproduced copies. When making changes or corrections, cross out the original entry with a single line, and initial and date the change. DO NOT ERASE, OVERWRITE, OR USE CORRECTION FLUID OR TAPE ON THE ORIGINAL.

Clinical data (including AEs, concomitant medications, and expected adverse reactions data) and clinical laboratory data will be entered into REDCap data system, a 21 CFR Part 11-compliant data capture system provided by NYU Langone Health. The data system includes password protection and internal quality checks, such as automatic range checks, to identify data that appear inconsistent, incomplete, or inaccurate. Clinical data will be entered directly from the source documents.

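### Blood pressure, lipids and Framingham score are tested as primary pre-post efficacy outcomes while routine cardiology care continues, and no planned analysis uses medication data

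*Combined protocol and SAP*

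**What the plan says.** Aim 1 (section 3.1) is to "Test the preliminary clinical efficacy of a PA promotion intervention on patients' cardiovascular risk profile". Section 4.2.1 lists among the primary endpoints "BMI, waist circumference, blood pressure, lipids and Framingham Heart Study Risk Score". The Protocol Summary states, under Reference Therapy: "This is a one-group study. There is no comparison group".

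Participants have cardiovascular disease or risk factors for it (Protocol Summary, Population). Section 6 describes the usual entry route: "After their visit with their cardiologist, interested patient subjects will have the study described". Section 6.1.2 then says: "Patient subjects will continue to see their cardiologists for routine clinical care according to their diagnosis". The eligibility criteria (5.1, 5.2) do not mention medication, and no section asks for it to be stable or to be tracked as a co-intervention.

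On analysis, section 9.1 says: "Paired t-tests will be used to assess changes in readiness to change number, the 6MWT, BMI, waist circumference, systolic and diastolic BP, lipids", with the Framingham score completing the list. The one regression in that section has change in physical activity as its outcome. The confounders named in sections 6.1.1 and 9.1 include no drug variable. Section 6.1.1 and the Schedule of Events (section 18) take clinical data from the health record at baseline only. Medication appears once, in section 13.1, where the data entered into REDCap are described: "Clinical data (including AEs, concomitant medications, and expected adverse reactions data".

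**The concern.** A paired t-test in one group measures everything that happened between the two visits. In a preventive cardiology clinic, part of that may be a change in blood-pressure or lipid treatment. The plan has no comparison group to absorb such a change and no analysis that would show it.

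The remote-collection rules in section 6.1.1 add to the exposure. Baseline lipids may be the most recent result on file and follow-up lipids the next one available, so the interval can be longer than three months and can span the index visit.

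At stake is how three of the primary outcomes are read. Section 9.2 says the pilot will supply preliminary effect sizes. A change produced partly by drugs could be carried forward as preliminary efficacy of the activity intervention and used to plan the next trial.

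**Working it through.** **1. The plan's own figure.** Section 9.3 gives 47 evaluable participants, 5% type 1 error, 80% power and a detectable effect size of 0.41. Sidedness is not stated.
- Attrition: 59 × 0.80 = 47.2, so 47.
- Normal approximation, two-sided: d = (1.960 + 0.842)/√47 = 2.802/6.856 = 0.409.
- Noncentral t, two-sided: d = 0.417.

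The stated 0.41 is reproduced with a two-sided test; 0.417 is used below.

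**2. Systolic pressure, on assumed inputs.** The documents give no drug-change rate, no effect per change and no SD of change. The assumed ranges are:
- share of participants with a pressure-lowering drug started or raised: 10-30%;
- fall in systolic pressure per change: 5-15 mmHg;
- SD of the before-after change: 12-15 mmHg.

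Mean shift with no activity effect = share × effect:
- low corner: 0.10 × 5 = 0.5 mmHg;
- middle: 0.20 × 10 = 2.0 mmHg;
- high corner: 0.30 × 15 = 4.5 mmHg.

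Detectable change = 0.417 × SD: 0.417 × 12 = 5.0 mmHg; 0.417 × 15 = 6.3 mmHg.

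Ratio of drug-driven shift to detectable change:
- low: 0.5/6.3 = 8% to 0.5/5.0 = 10%;
- middle: 2.0/6.3 = 32% to 2.0/5.0 = 40%;
- high: 4.5/6.3 = 71% to 4.5/5.0 = 90%.

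**3. What the planned test would do.** Let q be the share with a drug change and e its effect, in SDs of the outcome change among those without one. With no activity effect, the standardized mean change is d = q·e/√(1 + q(1−q)e²). For q = 0.30 and e = 1.0, d = 0.30/√1.21 = 0.273. Probability that the two-sided 5% paired t-test rejects at n = 47 (noncentral t):

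| e | q = 10% | q = 20% | q = 30% | q = 40% |
|---|---|---|---|---|
| 0.5 | 6% | 10% | 17% | 26% |
| 1.0 | 10% | 24% | 45% | 67% |
| 1.5 | 15% | 41% | 70% | 90% |

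Simulation of three cells agreed: 23.6% (e = 1.0, q = 20%), 44.6% (e = 1.0, q = 30%) and 70.5% (e = 1.5, q = 30%).

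**4. What is not quantified.** Steps 2 and 3 use assumed inputs only. No mg/dL figure is offered for lipids and none for the Framingham score. The protocol does not list the score's inputs, so the argument reaches it only as far as the chosen risk model uses blood pressure or lipids.

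**The case against.** The strongest reply is that the documents never say drugs will change. Section 6.1.2 says only that routine care goes on, and section 9.1 says the t-tests assess changes, without saying how those changes will be interpreted. The trial is a declared uncontrolled pilot with preliminary aims, and its sample size rests on the six-minute walk and activity measures. All of this is correct. It limits how firmly the point can be put, but the aim still uses the word efficacy for these outcomes.

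Four stronger readings are tempting, and the documents do not support them.
- **Drug changes acting over the whole window.** A reader might infer that everyone enrols straight from the visit. Section 5.4 also allows recruitment from a monthly list and by later telephone contact, and section 6.1.1 allows telephone consent. A change at the index visit need not coincide with baseline.
- **Drugs supplying most of the detectable change.** The 71-90% figure is the top corner of assumed ranges; the bottom corner is 8-10%. The calculation also assumes that every change lowers pressure, whereas a dose reduction would push the other way.
- **Medication data never captured, or no internal contrast at all.** Section 13.1 does mention concomitant medications. Section 9.1 also compares risk factors between those who do and do not achieve the activity recommendations. That comparison is unadjusted and is not specified as a comparison of changes, so it does not close the gap.
- **The subset without drug changes showing the activity effect.** That subset is selected on a post-baseline event. Drug decisions may follow blood pressure or lipid values, so it may over-represent patients already controlled or improving, and it drops anyone whose drug was reduced because of improvement. Without a control group it cannot isolate the activity effect.

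**Conclusion.** The point holds in a limited form. Three primary outcomes are tested before and after in one group, under continuing cardiology care, and no planned analysis uses medication data. If relevant drugs are changed during follow-up, these outcomes could move with no change in activity, and the plan as written could not show whether that happened.

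The size is unknown. On the assumed ranges, the shift in mean systolic pressure is 0.5-4.5 mmHg, or about 8-90% of what 47 completers can detect. The chance of a significant result with no activity effect runs from 6% to 90% across the illustrated scenarios. The conclusion rests on the inference that some drug changes will occur, not on any rate in the documents. It does not call the six-minute walk or step-count analyses into question. It should be addressed, as a matter of recording, one added table and wording.

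**What to change.** 1. In section 6.1.1 and the Schedule of Events, add a medication list at Time 1 and Time 2. Derive a flag for any start, stop or dose change of a blood-pressure- or lipid-lowering drug between them. Where remote rules apply, use the dates of the measurements actually analysed.
2. In section 9.1, report the proportion of participants with such a change.
3. Keep the paired analysis of all participants. Add a sensitivity table of blood pressure, lipid and Framingham changes in participants with no drug change.
4. State that all these results are pre-post changes, not effects of the activity intervention, and that the subset is not the sole basis for any statement about physical activity.

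This leaves care, eligibility, endpoints and sample size as they are. Section 13.1 already provides for entering concomitant medications, but start, stop and dose-change fields would have to be specified. The cost is a medication-list check at three months and a smaller subset. At the assumed 10-30% changed, the subset is 47 × 0.90 ≈ 42 down to 47 × 0.70 ≈ 33. The detectable effect size (normal approximation) then rises from 0.409 to 2.802/√42 = 0.43 and 2.802/√33 = 0.49.
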